### 1 Protocol Summary

### 1.1 Synopsis

**Protocol Title:** The Effect on Subjective Comfort of a Device Providing Positive Airway Pressure (PAP) Drops During Inspiration (TPAP) Compared to Continuous Positive Airway Pressure (CPAP) in Obstructive Sleep Apnea Patients

### Protocol Name/Number: TheraPAP Comfort

Phase: NA

Sponsor: SleepRes, LLC

**Rationale:** TheraPAP is a prototype device (with full documented electrical and isolation safety) being developed by SleepRes, LLC for the treatment of obstructive sleep apnea (OSA) that can deliver either standard CPAP at a set pressure or what is called TPAP. TPAP is a pressure control algorithm that lowers the pressure from the set pressure at the beginning of inspiration and does not return the pressure to the full set level until about halfway through expiration. The present study, TheraPAP Comfort, aims at assessing whether TPAP improves patient comfort vs. CPAP during supine wakefulness.

### **Overall Design:**

The TheraPAP Comfort Study is an in-office study to assess comfort of TPAP vs. CPAP in CPAP-naïve patients with OSA during supine wakefulness. Patients will be recruited after routine outpatient visits. They will be asked to breath normally for approximately 1 minute in supine wakefulness while being administered 2 different pressure therapies for comparison. For TPAP therapies, each baseline pressure (9 or 13 cmH2O) will consider 3 separate settings, TPAP A,TPAP B and TPAP C for 9, then TPAP D,TPAP E and TPAP F for 13.

At the first baseline pressure, patients will be asked to choose their preference between CPAP and TPAP A. This will be the primary endpoint. If TPAP A is chosen, testing will move on to the second baseline pressure. If CPAP is preferred, CPAP will then be compared to TPAP B. If TPAP B is chosen, testing will move on to the second baseline pressure. If CPAP is again chosen as preferred, it will be lastly compared to TPAP C, the latter two comparisons being secondary endpoints.

<sup>1 TPAP will be used herein to refer to the actual modified PAP delivery.

At the second baseline pressure, patients will be asked to choose their preference between CPAP and TPAP D. This will be the primary endpoint. If TPAP D is chosen, testing will move on to the second baseline pressure. If CPAP is preferred, CPAP will then be compared to TPAP E. If TPAP E is chosen, testing will move on to the second baseline pressure. If CPAP is again chosen as preferred, it will be lastly compared to TPAP F, the latter two comparisons being secondary endpoints.

Baseline CPAP (cmH2O)	TPAP Setting	Pressure Drop 1 (cmH 2 O)	Pressure Drop 2 (cmH 2 O)
	TPAP A	2	2
9	TPAP B	1	2
	TPAP C	1	1
	TPAP D	2	3
13	TPAP E	2	2
	TPAP F	1	2

**Table 1**. Pressure Drops 1 and 2 refer to the first and the second drops in pressure that occur during inspiration and are maintained until about halfway through expiration. The overall pressure drops consist of Drop 1+ Drop 2. CPAP, continuous positive airway pressure.

#### Number of Participants:

A total of 384 participants will be enrolled.

#### **Study Duration:**

The overall study duration for each participant will be up to a half hour including recruitment screening and testing.

# 1.2 Schedule of Activities (SoA)

Procedures	In-office study
Informed consent	Х
Demographics	Х
Height	Х
Weight	Х
Randomization	Х
In-office procedure	Х
AE/SAE monitoring	Х

 Table 2. Schedule of Activities for the TheraPAP Comfort Study.

Abbreviations: AE = adverse event; SAE = serious adverse event;

# 2 Introduction

### 2.1 Study Rationale

A therapy able to provide lower positive airway pressure (PAP) during inspiration than during expiration, designated TPAP, is being developed by SleepRes, LLC, for the treatment of obstructive sleep apnea (OSA). TPAP, as well as normal CPAP, are available on the SleepRes TheraPAP prototype device. In prior studies, the administration of higher inspiratory than expiratory PAP did not substantially increase treatment efficacy or adherence to continuous PAP (CPAP), which remains low. In our recent investigation, we demonstrated that the addition of a resistor to the CPAP circuit to reduce inspiratory PAP increased subjective comfort. The present study, TheraPAP Comfort, is an in-office study designed to examine whether TPAP at two different levels of pressure relief provides more subjective comfort than CPAP in awake supine participants.

### 2.2 Baseline

### 2.2.1 Obstructive Sleep Apnea

The National Commission on Sleep Disorders Research identified sleep disorders as a major public health burden. OSA is the most common of the more serious sleep disorders and affects approximately 20 million people in the United States (US), with approximately 13% of men and 6% of women affected (1). OSA is characterized by repetitive collapse or 'obstruction' of the pharyngeal airway during sleep, manifesting as repetitive episodes of hypopnea (i.e., shallow breathing) or apnea (i.e., paused breathing). These episodes of hypopnea or apnea may lead to hypoxemia, arousal from sleep, sleep fragmentation, excessive daytime sleepiness, and/or neuropsychological impairment.

Long-term, OSA is associated with increased mortality and a number of adverse cardiovascular, neurocognitive, metabolic, and daytime functioning consequences (2-11).

# 2.2.2 Unmet Medical Need

The large majority of OSA patients are treated with positive airway pressure, the most common of which is CPAP, provided by a machine that mechanically maintains an open airway. However, long-term adherence to therapy remains a challenge for many patients (12, 13). Common complaints include inconvenience, lack of perceived benefit, discomfort related to improper fitting of the interface, and difficulty expiring against positive pressure (14, 15).

As many patients cannot use CPAP because they find it intolerable, this represents a significant health concern, as OSA is associated with numerous adverse health outcomes and increased mortality. Strategies to improve tolerance of CPAP, and subsequently adherence, are needed.

# 2.2.3 Biological Rationale

TPAP is an innovative device/algorithm designed to deliver a lower inspiratory than expiratory PAP. The drop in inspiratory pressure can be modulated during the inspiratory phase. Previous research has shown that reducing inspiratory PAP by placing a resistor in the inspiratory line can enhance subjective comfort and decrease leaks when compared to CPAP, despite maintaining a similar residual apnea-hypopnea index (AHI). However, the resistor could only provide a fixed inspiratory PAP reduction based on existing PAP settings. TPAP addresses this limitation by allowing for adjustable drops in PAP throughout inspiration and part of expiration, offering a potentially more personalized and adaptive therapeutic approach.

	Endpoints
Primary	
 
CPAP vs. TPAP A at 9 cmH2O
 
CPAP vs. TPAP D at 13 cmH2O
 

Secondary	
 
CPAP vs. TPAP B at 9 cmH2O
 
CPAP vs. TPAP C at 9 cmH2O
 
CPAP vs. TPAP E at 9 cmH2O
 
CPAP vs. TPAP F at 9 cmH2O
 

Safety Endpoints	Spontaneous adverse events

# **3** Endpoints

Table 3. Summary of TheraPAP Comfort Study endpoints.

# 4 Study Design

# 4.1 Overall Design

The TheraPAP Comfort Study is an in-office study to assess patient-level comfort on TPAP vs. CPAP. Pre-screening is conducted to establish potential eligibility with a previous sleep study showing an AHI>10 events/hr. Eligible participants will undergo an in-office study in which they will breathe in the supine position during wakefulness on CPAP and on TPAP. In cases where CPAP is preferred, TPAP will be dropped to different levels based on the baseline CPAP levels, according to Table 1. CPAP and TPAP will be administered in one and in the opposite order per patient following a randomized design, to simulate patient blinding to treatment.

# 4.2 Detailed Design

# 4.2.1 Recruitment

Individuals deemed potentially eligible for enrollment based on the assessment of their medical data during a scheduled outpatient visit will be recruited once they arrive at the clinic to collect their CPAP equipment. Participants selected for eligibility will be naïve CPAP OSA consistently with enrollment criteria.

# 4.2.2 In-office study

Individuals who agree to participate will be asked to sign an informed consent prior to commencement of study procedures upon their arrival at the clinic.

The following activities will also occur:

- Height and weight will be measured.
- Randomization of CPAP/TPAP order.

To begin the study, each participant will lay in a supine position on a reclining chair in the office and all therapy comparisons will be made in this orientation. Subsequently, each patient will be studied on two different baseline positive pressures: 9 and 13 cmH2O. At either of the above pressures, each patient will assess CPAP against 2 different pressure drops in one-to-one comparisons.

For the baseline CPAP of 9 cmH2O, TPAP will be set to:

- TPAP A
- Followed by TPAP B if CPAP was previously preferred
- Followed by TPAP C if CPAP was previously preferred

For the baseline CPAP of 13 cmH2O, TPAP will be set to:

- TPAP D
- Followed by TPAP E if CPAP was previously preferred
- Followed by TPAP F if CPAP was previously preferred

Note that TPAP drops, designated as x/y, indicate first and second drop of PAP, starting during inspiration.

Assessment of comfort will be made by comparing one-to-one TPAP against each other or against CPAP by having the patient breathe on the pressure for one minute (or more as needed based on the judgment of the Study Coordinator) and then indicating which is more comfortable

by voice or hand sign. The indicated choice will be recorded by the Study Coordinator. The patient will be able to ask to repeat settings as often as needed to make the most informed choice.

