# 7.2 Randomization

All comparisons for each baseline pressure level (9 and 13 cmH2O) will be randomized separately for either baseline pressure per patient by using CPAP first in one case then CPAP second in the other. However, the baseline pressure order will not be randomized so that PAP-naïve patients can acclimate to PAP first at the lower pressure.

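### Section 4.2.2 lets exposure be extended or repeated with no equal-exposure rule within a pair and no record of it, so the preference endpoints are open to a bias of unknown direction and size

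*Combined protocol and SAP*

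**What the plan says.** The synopsis (Section 1.1, Overall Design) describes a short exposure: "They will be asked to breath normally for approximately 1 minute in supine wakefulness while being administered 2 different pressure therapies for comparison". Section 4.2.2 makes that one minute a minimum that may be lengthened, "or more as needed based on the judgment of the Study Coordinator", and adds: "The patient will be able to ask to repeat settings as often as needed to make the most informed choice". It gives no upper limit, no criterion for extending, and no rule that an extension or repeat must cover both pressures of the pair.

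The patient answers by voice or hand sign. On recording, Section 4.2.2 says: "The indicated choice will be recorded by the Study Coordinator".

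The sequence is adaptive. The synopsis says "If CPAP is preferred, CPAP will then be compared to TPAP B", and Section 4.2.2 repeats the rule: "Followed by TPAP B if CPAP was previously preferred". The same pattern applies at 13 cmH2O.

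Section 5.5, on minimising bias, offers only randomised order of CPAP within each comparison. Section 4.1 gives the purpose of that randomisation as "to simulate patient blinding to treatment". No section describes blinding of staff, a separate operator or a script. No section asks for exposure time or number of repeats to be recorded.

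**The concern.** Both primary endpoints (Table 3: CPAP against TPAP A at 9 cmH2O, and CPAP against TPAP D at 13 cmH2O) are subjective choices made after very brief exposure. To apply the adaptive rule, someone must translate the patient's answer into CPAP or TPAP before the next setting is chosen. With no staff blinding described, the people running the comparison probably know which pressure is which. Discretion over how long each pressure lasts, and over how the choice is elicited, may then be exercised with that knowledge.

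Randomised order balances what belongs to position, first or second. It does not balance what belongs to the therapy. If one therapy tends to get more time, or is presented differently, that difference remains in both orders and does not average out. Because nothing is logged, nobody could tell afterwards whether it had happened.

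**Working it through.** **The plan's own figure.** Section 7.1 gives 384 participants for 80% power at two-sided 5% with 6 comparisons, but states no expected preference share, so 384 can be neither confirmed nor refuted. What can be computed is the share that 384 choices would detect against 50%, using

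n = [z(1−α/2)·√(0.5·0.5) + z(0.80)·√(p(1−p))]² / (p − 0.5)².

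At α = 0.05 and p = 0.5715: (1.96 × 0.5 + 0.8416 × 0.4949)² / 0.0715² = 1.950 / 0.00511 ≈ 382, which fits within 384. The detectable share is therefore about 57.2%. It is about 57.9% at α = 0.025 and about 58.9% at α = 0.05/6.

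**Assumptions for the illustration.** The documents name no test, so I assume an exact two-sided binomial test against 50% at 5%. I also assume that all 384 participants give a choice. That is a maximum, because Section 7.1 allows a no-preference score. The net shifts are assumed; the documents give no basis for them.

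**Critical count.** The smallest c with 2·P(X ≥ c | 384, 0.5) ≤ 0.05 is 212 (p = 0.046; 211 gives 0.059). 212/384 = 55.2%, and 212 − 192 = 20 choices above the number expected with no preference.

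**Effect of a net shift when there is no true preference.** X ~ Binomial(384, 0.5 + b):

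| Net shift b | Share for the therapy that gains | Expected choices moved (384·b) | P(X ≥ 212) |
|---|---|---|---|
| 0 | 50% | 0 | 2.3% |
| 1 point | 51% | 3.8 | 5.5% |
| 2.5 points | 52.5% | 9.6 | 15.6% |
| 5 points | 55% | 19.2 | 48.8% |

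The table is symmetric: it applies to whichever therapy gains. A shift against TPAP would cost power instead. A true TPAP share of 57.2% gives P(X ≥ 212) = 0.80; a 2.2-point shift towards CPAP (57.2 − 2.2 = 55.0) lowers that to 0.488.

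**Sensitivity to the number analysed.** With only 64 choices (384/6), the critical count is 41, and a 5-point shift raises the upper tail from 1.6% to 9.1%. Fewer evaluable choices therefore weaken the inflation but do not remove it.

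**The case against.** The flexibility looks deliberate. CPAP-naïve patients may need more than a minute, and repeats exist so that the choice is an informed one. Repeats start with the patient, who is meant not to know which pressure is which and so has no label-based reason to favour either. This stands: the repeat route is weaker than the coordinator's discretion to extend, and one-sided repetition is permitted, not prescribed.

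A reader might infer that one unblinded coordinator times, repeats, interprets and records everything. The documents do not say so. Section 4.2.2 gives the Study Coordinator two tasks, judging duration and recording the choice. Section 5.4 places device use under an office coordinator, and the documents do not say whether that is the same person. Knowledge of the assignment is a reasonable inference from the adaptive rule, but it is not stated.

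A reader might also infer that extra time makes a therapy more comfortable, because Section 7.2 says that naïve patients "can acclimate to PAP first at the lower pressure". That sentence is about starting at 9 before 13 cmH2O, not about more time on one of two modes at the same baseline. Longer exposure could equally bring out discomfort; Section 4.2.2.1 lists uncomfortable breathing and claustrophobia as risks.

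The half-hour visit in Section 1.1 limits extension, but loosely. Two to six pairs at one minute per pressure take 2 × 2 = 4 to 6 × 2 = 12 minutes, leaving 18 to 26 minutes for screening, setup and any additional exposure.

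**Conclusion.** The concern holds as a risk of bias. The rule in Section 4.2.2 itself permits unequal exposure within a pair, staff probably know the assignment, randomised order does not correct a difference that follows the therapy, and no planned record would reveal one.

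It does not follow that the trial will be biased, or biased towards TPAP. Direction and size are unknown. The illustration shows only that a net shift of a few points is not negligible beside a detectable effect of about 7 points (57.2 − 50). It rests on an assumed test, an assumed 384 evaluable choices and assumed shifts. The conclusion about the wording of Section 4.2.2 depends on none of these.

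**What to change.** In Section 4.2.2:

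- State that any extension or repeat is given for both pressures of the pair, for the same time and in the randomised order, subject to the existing provision in Section 4.2.2.1 on interrupting procedures.
- Use a fixed, neutral script with the Pressure 1 / Pressure 2 labels already in Section 7.1, and record the answer in those terms.
- Record exposure time and number of repeats for each pressure, and tabulate both by therapy.

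If an analysis restricted to pairs without extension or repeat is added, label it descriptive. It selects on a post-randomisation event: pairs that needed no repeat are plausibly those with clear preferences, so a difference from the main result would not isolate exposure bias. The tabulation by therapy is more informative.

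These steps keep the repeats and make any imbalance visible. They limit prompting but do not blind the staff. The cost is a few extra minutes in some pairs and two more data fields, with no additional staff and no change to the device or the sample size.

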# 4.2.2.1 Risk-benefit Analysis

The procedures involved in the studies include minimal risk, i.e., related to very short-term TPAP or CPAP administration (e.g., uncomfortable breathing, claustrophobia, lightheadedness, etc.). Upon experiencing any discomfort by the participant, the procedures will be interrupted.

There is no direct benefit or treatment to the participants, however the results of the study can potentially yield future benefit to the participants in terms of wider treatment alternatives for their OSA.

# 4.3 End of Study Definition

A participant is considered to have completed the study if they have completed all TPAP and CPAP administration.

# 5 Study Population

Eligible participants will be recruited from the existing clinic population at the study site. Participants must be able to provide written consent and meet all the inclusion criteria and none of the exclusion criteria.

# 5.1 Inclusion Criteria

### Age and Sex

1. Between 18 to 70 years of age, inclusive.

### **OSA Measures**

- 2. AHI > 10 on a previous HST.
- 3. CPAP naïve individuals

### Weight

4. BMI above  $18 \text{ kg/m}^2$ , inclusive.

### **Informed Consent**

- 5. Participant voluntarily agrees to participate in this study and signs an Institutional Review Board (IRB)-approved informed consent prior to performing any of the study-related procedures.
- 6. Participant must be able to understand the nature of the study and must have the opportunity to have any questions answered.

# 5.2 Exclusion Criteria

Participants are excluded from the study if any of the following criteria apply:

- 1. Any non-previously mentioned vulnerable population.
- 2. Any condition that in the investigator's opinion would present an unreasonable risk to the participant, or which would interfere with their participation in the study or confound study interpretation.
- 3. Any chronic lung diseases.
- 4. Patients with hypoglossal nerve stimulation implant.
- 5. Chronic oxygen therapy.
- 6. A serious illness or infection in the past 30 days as determined by investigator.

### 5.3 Screen Failures

By definition, patients that do not meet the inclusion/exclusion criteria at the outpatient screening visit, will not be invited to or further contacted to participate in the study.

### 5.4 Preparation/Handling/Storage/Accountability

Prototype TheraPAP devices will be provided by the sponsor and will be kept in locked location when not in use. These devices will be used only for approved study purposes as designated by the office coordinator who will oversee their use in the office.

# 5.5 Measures to Minimize Bias

The order of CPAP tested first or second for each of the comparative tests for each baseline pressure will be randomized per patient, although the order of baseline pressure will be maintained for each patient starting with 9 cmH2O, then moving to 13 cmH2O.

# 5.6 Concomitant Therapy

Usual therapy is allowed as per the participants' physicians' indications, except for oxygen therapy that constitutes an exclusion criterion.

# 5.7 Discontinuation of Study Treatment

If a clinically significant finding is identified, the Investigator or qualified designee will determine if the participant can continue in the study and if any change in participant management is needed. Any new clinically relevant finding should be reported as an adverse event (AE).

# 5.8 Stopping Criteria

# 5.8.1 Individual Participant Stopping Criteria

Participants reporting any SAE considered possibly related or related to study device will be withdrawn from the study.

Any other AE that in the judgment of the Investigator necessitates the participant stopping to protect participant safety, will result in early withdrawal from the study.

# 5.9 Participant Discontinuation/Withdrawal from the Study

A participant may withdraw from the study at any time at his/her own request or may be withdrawn at any time at the discretion of the Investigator for safety, behavioral, or administrative reasons.

If the participant withdraws consent, the Sponsor may retain and continue to use any data collected before such a withdrawal of consent.

All participants who withdraw from the study with an ongoing AE must be followed until the event is resolved or deemed stable.

Participation may be terminated before completing the study and the reason recorded as follows:

- Withdrawal due to AE
- Participant withdrew consent at own request (e.g., due to intolerance to study procedures)
- At the discretion of the Investigator for safety, behavioral, or administrative reasons.
- o Other

### 5.10 Participant compensation

Participants will be compensated for their time and participation with a free V-Com™ (approximately \$30 value) upon full completion of the study.

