Appendix 3.

Adverse events will be reported by the participant.

The Investigator and any qualified designees are responsible for detecting, documenting, and reporting events that meet the definition of an AE or SAE and remain responsible for following up on AEs that are serious, considered related to the study device or the study, or that caused the participant to discontinue the study.

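### Compensation depends on finishing every administration, so a participant who stops because of symptoms receives nothing, a modest and cheaply removed reason to continue or stay silent

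*Combined protocol and SAP*

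**What the plan says.** Five parts of the protocol bear on this.

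- **Compensation (5.10).** Participants receive a V-Com device, valued at about $30, "upon full completion of the study". No partial or alternative compensation is described.
- **Completion (4.3).** "A participant is considered to have completed the study if they have completed all TPAP and CPAP administration".
- **Discomfort (4.2.2.1).** The expected risks are given as "uncomfortable breathing, claustrophobia, lightheadedness, etc". The rule is: "Upon experiencing any discomfort by the participant, the procedures will be interrupted". The section does not say whether an interruption is a pause or an end. It also says that participants get no direct benefit from taking part.
- **Early ending (5.8.1, 5.9).** A serious adverse event at least possibly related to the device leads to withdrawal. Any other adverse event does so only if the investigator judges that stopping is needed. Section 5.9 adds "A participant may withdraw from the study at any time at his/her own request", and its reasons for termination before completion include an adverse event and intolerance of the procedures.
- **Safety data (Table 3, 6.3, 6.3.2).** The only safety endpoint is "Spontaneous adverse events". Section 6.3 states: "Adverse events will be reported by the participant". It also makes the investigator and designees responsible for detecting events, and Section 6.3.2 prefers open-ended, non-leading questions.

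**The concern.** The events expected here are mild, brief and subjective, so they enter the data mainly if the participant mentions them. Under 5.10 and 4.3, a participant who stops because of such an event loses the only tangible return that the protocol describes. Someone who feels claustrophobic or lightheaded therefore has some reason to carry on, or to say nothing until the session is over.

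Two things are at stake. The first is the count of adverse events, which is all the safety evidence that the study will produce. The second is the right to withdraw at any time, which remains in force but carries a cost if used before the end.

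The condition also fits poorly with the stated purpose of the compensation, which is to recognise time and participation. A participant who consents, is randomized, breathes on the device and then stops has given both.

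**Working it through.** **Step 1. Set the rules side by side.** The plan states no figure for this point, so the check is mainly one of text.

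| Situation | Rule that applies | Completed under 4.3? | Item under 5.10? |
|---|---|---|---|
| Reports discomfort, is interrupted, resumes and finishes | 4.2.2.1 | Yes | Yes |
| Reports discomfort only after the last comparison | 6.3.1 (events collected to the end of the study) | Yes | Yes |
| Chooses to stop because of intolerance | 5.9 | No | No |
| Withdrawn because the investigator judges that an adverse event requires it | 5.8.1 | No | No |
| Withdrawn for a serious event at least possibly related to the device | 5.8.1 | No | No |

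The loss is therefore attached to stopping, not to reporting. A participant cannot be sure in advance which row will apply, because 4.2.2.1 does not say what follows an interruption.

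**Step 2. Note the order of testing.** Sections 5.5 and 7.2 fix the order as 9 and then 13 cmH2O. A CPAP-naïve participant who is uncomfortable at 9 must go on to the higher pressure to qualify for the item.

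**Step 3. Illustrate what withheld reports would do.** The documents give neither an event rate nor a withholding rate, so both are assumptions. Recorded events = 384 × true rate × (1 − share withheld), with 384 from the synopsis.

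| Assumed true rate | None withheld | 25% withheld | 50% withheld |
|---|---|---|---|
| 1% | 3.8 | 2.9 | 1.9 |
| 3% | 11.5 | 8.6 | 5.8 |
| 5% | 19.2 | 14.4 | 9.6 |
| 10% | 38.4 | 28.8 | 19.2 |

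The table shows the direction of a possible error and its arithmetic. It is not an estimate for this trial.

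**Step 4. Cost of removing the condition.** Cost = 384 × assumed share stopping early × $30 (value from 5.10).

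- 5%: 384 × 0.05 = 19.2 participants; 19.2 × $30 = $576.
- 10%: 384 × 0.10 = 38.4 participants; 38.4 × $30 = $1,152.

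**The case against.** The strongest reply is that the text does not penalise reporting. A reader might infer from 4.2.2.1 and 5.10 together that anyone who reports discomfort loses the item. The documents do not support that. The word used is interrupted, and 5.8.1 requires withdrawal only for a serious event at least possibly related to the device, or where the investigator judges stopping necessary. Section 4.2.2 lets settings run longer and be repeated as needed, which fits a pause. A participant can report a mild symptom, resume, finish and be compensated. This part of the objection stands.

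Second, there are safeguards. Staff share responsibility for detecting events, questioning is open-ended, and a report made after the last comparison costs nothing. This stands as partial mitigation. Open-ended questions still depend on disclosure, and they do not help someone who stays on the device in order to finish.

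Third, the incentive is small: an item worth about $30, for a visit of up to half an hour described as minimal risk. This also stands, and it is why the effect can be called only modest and of unknown size.

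Fourth, a reader might infer that participants who want to finish will answer carelessly and so add noise to both primary endpoints. The documents do not show this. Compensation does not depend on which pressure is preferred, the 9 cmH2O primary is the first comparison of the session, and a wish to finish quickly could exist without the condition.

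Finally, the consent material is not part of the public text and may already deal with early stopping. No claim is made here about what it says. What the objections leave untouched is the rule in 5.10 itself, under which a person who stops for symptoms receives nothing.

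**Conclusion.** The point holds as a narrow one. On the protocol's own wording, ending participation early for an adverse event or intolerance forfeits all compensation. This follows from rules that the plan states, not from missing detail. It creates a foreseeable reason to continue through discomfort, or to delay or withhold reports, and any resulting error in the sole safety endpoint would be downward. Whether such an error would occur, and how large it would be, cannot be determined from the documents; the event and withholding rates used above are assumptions. No effect on the primary endpoints is established, and none is claimed.

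This is a cheap improvement. The case for it rests on the low cost of removing the incentive, not on a demonstrated bias.

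**What to change.** Change Section 5.10 so that every participant who consents and starts the in-office procedure receives the compensation, including anyone who stops early because of an adverse event, discomfort or intolerance. Make the participant information consistent with this, so that participants know before they start that stopping or speaking up costs them nothing.

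The change is one sentence in the protocol, with matching wording in the participant information if it is not already there, plus IRB approval of the amended text. The running cost is about $30 for each early stopper. No endpoint, sample size, pressure setting or stopping rule is altered. Giving part of the item's value, or compensating only stops related to adverse events, would also weaken the incentive. Compensating everyone who starts is simpler, because nobody has to decide why a participant stopped or whether an interruption counted as non-completion.
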